**Title: Evaluation of WIRION™ EPS in Lower Extremities Arteries**

Document No. CL-003

Version 2.2

Page 1 of 4

**WISE LE Study protocol synopsis dated July 20 2016  
NCT02780349**

Title:	WISE LE: Evaluation of WIRION™ EPS in Lower Extremities Arteries
Study Objective	Demonstrate the safety and performance of the WIRION™ EPS in subjects undergoing lower extremity atherectomy for the treatment of Peripheral Arterial Disease (PAD).
Study Design	Prospective, multi-center, non-randomized, open label, single arm study. Up to 153 consented subjects who undergo atherectomy due to lower limb PAD will be enrolled. All subjects will undergo baseline assessment, intervention (atherectomy in conjunction with WIRION™ EPS) and post procedure follow up. All subjects will have a follow up visit at 30±7 days post procedure. Results will be compared to a performance goal based on an analysis of previous trials that studied atherectomy with an embolic protection filter in similar patient cohorts.
Study Population:	
Both male and female subjects who meet all the eligibility criteria and give written informed consent will be enrolled in the study.
 
Inclusion Criteria
 
 
1) Subject is at least 18 years of age
 
2) Subject or authorized representative, signed a written Informed Consent form to participate in the study, prior to any study related procedures
 
3) Subject is willing to comply with the protocol requirements and return to the treatment center for all required clinical evaluations
 
4) Rutherford classification 2-4
 
5) Has moderate to severe calcification visualized on angiogram in the femoropopliteal arteries
 
6) Planned atherectomy of the native femoropopliteal arteries
 
7) Reference vessel diameter for intended filter location must be visually estimated to be ≥3.5mm and ≤6.0mm
 
8) An adequate “landing zone” for placement of the WIRION™ device distal to the target lesion of at least 30mm
 
9) A female subject is eligible if not of child bearing potential or has a negative pregnancy test within the previous 7 days and agrees to remain on birth control throughout the study
 
 
Exclusion Criteria
 
 
1) Any planned surgical or endovascular intervention within 30 days before or after the index procedure
 
2) A lesion deemed not accessible by the WIRION™ EPS
 
3) Inability to take aspirin or ADP receptor antagonists
 
4) History of bleeding diathesis or coagulopathy or will refuse blood transfusion if deemed necessary
 

**Title: Evaluation of WIRION™ EPS in Lower Extremities Arteries**

Document No. CL-003

Version 2.2

Page 2 of 4

	
 
5) Has perforation, dissection, or other injury of the access or target vessel requiring additional stenting or surgical intervention before enrollment
 
6) Subject is enrolled in another drug or device study protocol that has not reached its primary endpoint (participating in registry studies is not excluded)
 
7) Life expectancy less than 12 months
 
8) Known severe renal insufficiency (eGFR <30 ml/min/1.72m^2).
 
9) ≤1-vessel tibial run-off status
 

Number of subjects:	Up to 153 with an interim analysis after 100 subjects
Clinical sites:	Up to 10 sites; up to 1/3 of the study patients at OUS sites
Investigational Product:	WIRION™ Embolic Protection System (Gardia Medical Ltd.)
Primary end point	
Freedom from major adverse events (MAE) to 30 days post procedure.
 
MAE defined as a serious adverse event that results in death, acute myocardial infarction, thrombosis, pseudo-aneurysm, dissection (grade C or greater) or clinical perforation at the filter location, distal embolism (clinically relevant), unplanned amputation, or clinically-driven target vessel revascularization (TVR), through 30 days post-procedure, as adjudicated by the Clinical Events Committee (CEC).

Secondary end points	
 
• Device success Defined as: 
 
- A successful delivery and deployment of WIRION™ distal to the intervention site without complications, AND
 
- Successful retrieval of WIRION™ following completion of the stenting procedure, without complications
 
 
 
• Clinical success Defined as: Device success with freedom from procedure related serious adverse events ascribed to the WIRION
 
• Technical success Defined as: Freedom from device malfunctioning causing the procedure to be aborted
 
• Percent of filters with visible debris
 

Assessment Schedule:	
Baseline Visit:
 
 
a) Eligibility according to inclusion and exclusion criteria
 
b) Obtaining signed Informed Consent Form (ICF)
 
c) Demographics (sex, year of birth, smoking status)
 
d) Risk factors & medical history
 
e) Concomitant medications
 
f) Disease oriented physical examination including vital signs (weight, height, BMI, heart rate, blood pressure) and ABI (except in cases
 

	
where blood pressure cuff occlusion of the extremity is contraindicated)
 
 
g) Blood test including: RBC, Hemoglobin, WBC, Platelet count, PT, aPTT, INR, serum creatine-kinase isoform MB (CK-MB) and serum creatinine
 
h) Pregnancy test, if applicable
 
i) Safety evaluation (AE/SAE evaluation)
 
 
Intervention (Use of WIRION™):
 
 
a) Investigational procedure & materials (atherectomy device, EPS, guide wires and contrast medium)
 
b) Intervention details (investigator name, procedure duration and fluoroscopy time)
 
c) Angiography of target lesion
 
d) Dilation after atherectomy
 
e) Stent placement after atherectomy
 
f) Angiographic assessment of visible distal embolization, as evidenced by new angiographic filling defect, slow flow, and/or loss of distal tibial runoff
 
g) AE/SAE
 
h) Usability questionnaire
 
i) Visual assessment of debris in the filter
 
j) Concomitant medications
 
 
Pre-Discharge Follow-up:
 
 
a) Disease oriented physical exam including vital signs (heart rate and blood pressure) and ABI (except in cases where blood pressure cuff occlusion of the extremity is contraindicated)
 
b) AE/SAE evaluation
 
c) Blood test including: RBC, Hemoglobin, WBC, Platelet count, PT, aPTT, INR and serum creatine-kinase isoform MB (CK-MB) and serum creatinine
 
d) Concomitant medications
 
 
End-of-Study Follow-up Visit (30±7 days post procedure):
 
 
a) AE/SAE evaluation
 
b) Disease oriented physical exam including vital signs (heart rate and blood pressure) and ABI (except in cases where blood pressure cuff occlusion of the extremity is contraindicated)
 


Statistical Considerations:
	
A performance goal group sequential design with a maximum of two stages with rejection boundaries according to Lan-DeMets alpha spending function with O’Brien- Fleming boundaries. The expected proportion of subjects who would meet the primary endpoint if treated according to current clinical practice is 10.7%. This performance goal is based on the DEFINITVE LE and DEFINITVE Ca++ trials.
 
The study is designed to test the primary null hypothesis that the 30-day MAE outcome using the WIRION™ EPS in conjunction with atherectomy is equal to or higher than the PG of 19.26%, as opposed to the alternative hypothesis that the MAE is less than this PG. An interim analysis will be carried out when

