**Title: Evaluation of WIRION™ EPS in Lower Extremities Arteries**

Document No. CL-003

Version 2.2

Page 4 of 4

	
100 (68.5%) of the originally planned subjects have reached the 30-day follow-up. Using an Exact Binomial Test and under the following assumptions:
 
Alpha (one-sided) = 0.025 <math>\beta</math>= 0.20 PE= 10.7% Performance goal= 19.26%
 
An estimated 145 evaluable subjects will be required for 80% power if the study reaches the final analysis. With an anticipated combined loss-to-follow-up of up to 5%, 153 patients will be enrolled in the study.
 
An interim analysis will be performed when 100 subjects (approximately 68.5% of the 145 evaluable subjects) have completed the study; two potential options will be pursued:
 
The study will be stopped for efficacy if the primary null hypothesis is rejected at one sided alpha = 0.0068 based on the Lan-DeMets alpha spending function with O'Brien - Fleming boundaries.
 
If based on the interim analysis the primary null hypothesis cannot be rejected, then the trial will continue to a total sample size of 153 enrolled subjects (i.e., 145 evaluable subjects). This test will be conducted at one-sided alpha = 0.0229, in order to control the overall Type I error at 2.5%.
 
Study success is defined as rejecting the null hypothesis.

Duration of Study	The estimated study duration is ten months, including a recruitment phase and follow up period of 30±7 days

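### Should visible distal embolization, which is recorded at every procedure, have been a named endpoint with its own analysis?

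*Combined protocol and SAP*

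**What the plan says.** The Study Objective is to "Demonstrate the safety and performance of the WIRION™ EPS in subjects undergoing lower extremity atherectomy".

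Under Assessment Schedule, Intervention, item f is "Angiographic assessment of visible distal embolization, as evidenced by new angiographic filling defect, slow flow, and/or loss of distal tibial runoff" and item i is "Visual assessment of debris in the filter". Item g collects adverse events at the same procedure.

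Secondary end points lists four measures:

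- device success, whose first limb is "A successful delivery and deployment of WIRION™ distal to the intervention site without complications" and whose second limb is uncomplicated retrieval;
- clinical success, "Device success with freedom from procedure related serious adverse events ascribed to the WIRION";
- technical success, meaning no malfunction that aborts the procedure;
- "Percent of filters with visible debris".

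The Primary end point counts distal embolism only when it is clinically relevant, a serious adverse event, and adjudicated by the Clinical Events Committee. Statistical Considerations gives an analysis for 30-day MAE alone and ties study success to that test.

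**The concern.** Items f and i are parallel observations at the same procedure. Debris in the filter became an endpoint and visible embolization did not. Debris shows what the filter held, while item f is the scheduled assessment closest to what it did not hold. The performance half of the objective could therefore be reported with the first figure and without the second, and the decision to report item f could be made after the results are known.

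A non-serious filling defect or slow flow satisfies item f but cannot be an MAE. It may be recorded as an adverse event. Whether it also fails device success, and through it clinical success, depends on what counts as a complication, which the synopsis does not define. Nor does the synopsis say whether item f is read with the filter in place or after retrieval, or who reads it. At stake would be the completeness and consistency of the descriptive performance results.

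**Working it through.** **1. Does the point touch the primary analysis?** Inputs from Statistical Considerations: goal 19.26%, expected MAE rate 10.7%, one-sided alpha 0.025 (0.0068 at 100 subjects, 0.0229 at the end), 145 evaluable, 5% loss.

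- Exact binomial at n = 145: the null is rejected with 18 or fewer MAEs. P(X ≤ 18 | 0.1926) = 0.0196; P(X ≤ 18 | 0.107) = 79.2%.
- Two-stage rule (9 or fewer of 100, then 18 or fewer of 145): overall alpha 0.0207, power 79.6%.
- Enrolment: 145 / 0.95 = 152.6, rounded up to 153.

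The sizing reproduces, and no embolization figure enters it.

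**2. Is item f treated differently from its neighbours?**

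| Measure | Collected | Named endpoint | Analysis stated in synopsis |
|---|---|---|---|
| 30-day MAE | yes | primary | yes |
| Device, clinical, technical success | yes | secondary | no |
| Filters with debris | yes | secondary | no |
| Visible embolization (item f) | yes | no | no |
| ABI, CK-MB, creatinine, fluoroscopy time, usability | yes | no | no |

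The lack of an analysis is common to every secondary measure. What is particular to item f is only its absence from the endpoint list, and it shares that with several other collected items.

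**3. What would an analyst report, and how much does discretion matter?** The natural base is every subject in whom the device was attempted, up to 153. The documents give no rate, so the counts x are assumed. The exact 95% interval runs from the 2.5% quantile of Beta(x, n−x+1) to the 97.5% quantile of Beta(x+1, n−x).

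| Assumed events | n = 153 | n = 145 |
|---|---|---|
| 0 | 0% (0 to 2.4%) | 0% (0 to 2.5%) |
| 3 | 2.0% (0.4 to 5.6%) | 2.1% (0.4 to 5.9%) |
| 7 | 4.6% (1.9 to 9.2%) | 4.8% (2.0 to 9.7%) |

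Choosing the follow-up base over the treated base moves the estimate by 0.2 points at most.

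**4. If the trial stops at the interim.** The 100 subjects there are those with 30-day follow-up, so 100 is a minimum for a procedural outcome. With 5% loss, about 100 / 0.95 = 105 would have been treated to yield them. Assume also no enrolment pause and even enrolment over nine of the ten months, 153 / 9 = 17 a month. Another 17 (30 days) to 21 (37 days) would then have been treated, giving 122 to 126. With 0 events the upper limit, 1 − 0.025^(1/n), is 3.6% at 100, 3.0% at 122 and 2.9% at 126.

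**5. The undefined complication.** With 7 assumed non-serious events in 153 and no other failure, device success is 153/153 = 100% (97.6 to 100%) if none counts, and 146/153 = 95.4% (90.8 to 98.1%) if all count. The definition attaches complications to delivery and deployment and to retrieval. An embolization during atherectomy, with the filter already deployed, belongs to neither step on a plain reading. The full 4.6-point gap arises only if all seven are treated as complications of one of those steps.

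**The case for a change.** The strongest case for a change is that a filter exists to prevent distal embolization. The sponsor schedules the assessment, defines its signs, and then commits to reporting only the debris. The primary composite admits only serious adjudicated events and yields no separate embolization rate. Adverse event tables are not a proportion with a fixed definition, time point and base. Naming the measure in advance would cost one line and one table, would add no procedure, and would remove any choice about reporting it once the result is known.

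Much of this stands. The measure is not on the endpoint list, and committing to it beforehand would be tidier. But it asks the plan to write down something left out and corrects no error. Counting the clinically relevant form of embolism, and not an angiographic sign, is a defensible design choice. The gain is also modest: the percentage of filters with debris is not a capture rate, so a per-subject embolization rate beside it would not give filter efficiency, and an item f event does not prove filter failure. Reading time, reader and the meaning of a complication are details that a four-page synopsis may leave to fuller documents. Inconsistent scoring between sites is possible, but nothing in the synopsis shows it, since it does not say who scores device success.

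**Conclusion.** No change is needed. This is a gap that analysts fill sensibly: the proportion of treated subjects with an item f event, with an exact interval, can be produced from data already scheduled. Discretion over the base shifts it by about 0.2 points in the illustrations. The largest visible effect, 100% against 95.4% device success, rests on an assumed count of seven and on a reading of complications broader than the definition suggests.

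Following the plan as written leaves the MAE result and the study conclusion sound. A descriptive table beside the debris endpoint, with a note on whether item f events count as complications, is optional. If one is produced, it should be described as visible embolization at the procedure. This conclusion is limited to what the synopsis states, and the event counts are assumptions.

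### The primary endpoint runs through day 30, but the last scheduled contact may fall on day 23 and no later status check is required

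*Combined protocol and SAP*

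**What the plan says.** Under Primary end point, the outcome is "Freedom from major adverse events (MAE) to 30 days post procedure", and MAEs are counted "through 30 days post-procedure, as adjudicated by the Clinical Events Committee (CEC").

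Under Study Design, "All subjects will have a follow up visit at 30±7 days post procedure". The Assessment Schedule lists the same visit as the last one, under the label "End-of-Study Follow-up Visit (30±7 days post procedure"). Nothing is scheduled between it and the pre-discharge assessment. Duration of Study describes the study as "including a recruitment phase and follow up period of 30±7 days", so the window applies to the follow-up period as well as to the visit.

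Statistical Considerations specifies an exact binomial test. The interim look comes when 100 "of the originally planned subjects have reached the 30-day follow-up"; a later paragraph of the same section makes it 100 subjects who have completed the study. The section requires 145 evaluable subjects but does not define evaluable, and it sets no minimum follow-up for an event-free subject.

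**The concern.** The endpoint has a fixed 30-day horizon, while observation may end up to a week earlier with no protocol deviation. A binomial count records each subject as MAE or no MAE and cannot allow for days that were not observed.

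The error has one direction. Success means showing an MAE rate below 19.26%, and an unrecorded event makes that easier. With no concurrent control arm, an under-count is not shared by a comparison group. The earlier trials behind the performance goal may have had similar windows, but the synopsis does not say, so cancellation cannot be assumed.

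The interim look is exposed too. A day-23 visit satisfies both wordings of the trigger, so the study could stop for efficacy on incomplete risk periods.

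**Working it through.** **Inputs (Statistical Considerations).** Performance goal p0 = 19.26%; expected MAE rate p1 = 10.7%; one-sided alpha 0.025 overall, 0.0068 at the interim (n = 100) and 0.0229 at the final analysis (n = 145); 5% loss; 153 enrolled. The window comes from the Assessment Schedule: 30 − 7 = day 23 to 30 + 7 = day 37.

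**Step 1: reproduce the design.** The boundary is the largest MAE count c with P(X ≤ c | n, p0) no greater than the alpha for that look.

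- Interim: P(X ≤ 9 | 100) = 0.0039 and P(X ≤ 10 | 100) = 0.0092, so success needs at most 9 MAEs.
- Final: P(X ≤ 18 | 145) = 0.0196 and P(X ≤ 19 | 145) = 0.0336, so success needs at most 18 MAEs.

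The two-stage success probability at rate p is P(X1 ≤ 9) + Σ P(X1 = x)·P(X2 ≤ 18 − x), summed over x = 10 to 18, with X1 from 100 subjects and X2 from the next 45. It is 2.07% at 19.26% and 79.6% at 10.7%. Enrolment is 145/0.95 = 153. The planned 80% power and sample size are therefore reproduced.

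**Step 2: effect of missed events.** Let m be the share of 30-day MAEs missed because they follow an early last visit. The observed rate is then 0.1926 × (1 − m). The documents do not give m, so the values below are assumptions.

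| m | Two-stage type I error |
|---|---|
| 0 | 2.07% |
| 1% | 2.37% |
| 1.41% | 2.50% |
| 2% | 2.70% |
| 5% | 3.95% |

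Expected MAEs at the goal are 145 × 0.1926 = 27.9. The share that uses up the margin is 0.0141 × 27.9 = 0.39 of an event.

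**Step 3: what the window could imply.** Assume visits spread evenly over the 15 days from 23 to 37. Unobserved days sum to 7 + 6 + 5 + 4 + 3 + 2 + 1 = 28, so the unobserved share of the risk period is 28/(15 × 30) = 6.2%. Assume further that a fraction f of MAEs occurs at a constant rate over 30 days, that the rest occur early, and that events after an early visit go unrecorded. Then m = 0.0622 × f.

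| f | m | Two-stage type I error |
|---|---|---|
| 20% | 1.24% | 2.45% |
| 30% | 1.87% | 2.65% |
| 50% | 3.11% | 3.11% |
| 100% | 6.22% | 4.58% |

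The 2.5% line is crossed at f = 0.0141/0.0622 = 23%. The last row is the limit for this visit pattern, not an estimate.

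**The case against.** The strongest reply is that the document is a four-page synopsis. Rules on SAE reporting, evaluability and missing outcomes usually sit in fuller documents. The MAE definition already fixes the window at 30 days whatever the visit date, and no text says that event capture stops at an early visit. This stands as a limit on what can be concluded. If another document requires day-30 status, the sponsor can cite it. It does not remove the gap in the supplied text, where the visit ends the study and the follow-up period itself is 30±7 days.

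The illustration can also be challenged. Visits aimed at day 30 should cluster there. With a triangular spread over the same window (weights 1 to 8 and back to 1, total 64), the unobserved share is 84/64/30 = 4.4%. The crossing then moves to 0.0141/0.0438 = 32% late events, and 30% late events gives 2.47%. Several MAE components, such as dissection or perforation at the filter location, arise around the procedure, so the all-late case is a bound. Both remarks are fair. They affect the size, not the direction, and death, myocardial infarction, amputation and revascularization can all occur later.

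Finally, similar windows in the trials behind the goal would largely cancel the bias. That is possible, but the documents give no basis for relying on it.

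**Conclusion.** The concern holds. As written, the plan lets a compliant subject leave before the endpoint period ends and be counted as event-free, and the resulting error can only favour success.

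Its size cannot be determined from the documents. It is nil if every MAE precedes the last visit or is captured in some other way. No figure in the documents shows that the nominal 2.5% is exceeded. The margin is thin, however: exact type I error rises from 2.07% to 2.5% once 1.4% of MAEs are missed. Whether that happens depends on assumed visit patterns and event timing, with the crossing at about 23% late events for evenly spread visits and about 32% for visits peaked at day 30. The change should be made because the risk is one-sided and cheap to remove.

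**What to change.** Keep 30±7 days for the examination and add two rules:

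- If the last visit takes place before day 30, MAE status through day 30 is confirmed by a contact on or after day 30.
- At both the interim and final analyses, a subject counts as event-free only when MAE status is known on or after day 30. MAEs dated after day 30 do not count, in line with the existing endpoint definition.

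Alternatively, open the final ascertainment window at day 30, for example day 30 to 44, which keeps the 14-day width and needs no extra contact.

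Report how many subjects lack status on or after day 30, with a sensitivity analysis that counts them as event-free. Setting aside only event-free subjects with unknown status raises the observed rate slightly: 18/145 = 12.4% against 18/153 = 11.8%.

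**Cost.** Sample size, alphas and boundaries are unchanged. With evenly spread visits, 7/15 × 153 = about 71 subjects need a brief contact; under the alternative, follow-up ends about a week later for the last subjects. Subjects seen early and not reached again draw on the loss allowance of 153 − 145 = 8. If that allowance were already used and 10% of the 71 (about 7) were not reached, 138 would be evaluable. The final boundary would then be 17 and two-stage power about 78%.

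### Does the mislabelled 10.7%, and the unexplained step from it to 19.26%, leave the trial's performance goal unclear?

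*Combined protocol and SAP*

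**What the plan says.** The Primary end point row defines the outcome as "Freedom from major adverse events (MAE) to 30 days post procedure". A subject who meets the endpoint has therefore had no MAE.

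The first paragraph of Statistical Considerations gives the proportion who "would meet the primary endpoint if treated according to current clinical practice is 10.7%. This performance goal is based on" two named earlier trials. The next paragraph sets the null hypothesis: the 30-day MAE rate "is equal to or higher than the PG of 19.26" per cent, with a lower rate as the alternative. The sample-size inputs on the last page read "PE= 10.7% Performance goal= 19.26" per cent. PE is not spelled out.

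The decision rules follow. At 100 subjects, "The study will be stopped for efficacy if the primary null hypothesis is rejected at one sided alpha = 0.0068". If the trial continues to 145 evaluable subjects, "This test will be conducted at one-sided alpha = 0.0229". Finally, "Study success is defined as rejecting the null hypothesis".

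On the origin of the goal, the Study Design row says: "Results will be compared to a performance goal based on an analysis of previous trials". No section shows the calculation that leads to 19.26%.

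**The concern.** In a single-arm trial the performance goal is the only comparator, so a reader should be able to see what it is and where it comes from. Three things stand in the way.

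- **Direction.** Taken with the freedom-from-MAE endpoint, the sentence implies that 89.3% of patients on current practice have an MAE within 30 days.
- **Label.** The words about the performance goal come straight after 10.7%, the only figure given up to that point. The goal tested is 19.26%. A reader cannot tell whether the earlier trials support 10.7%, 19.26% or both.
- **Derivation.** The goal lies 19.26 − 10.7 = 8.56 points above the expected rate, and no reason for that distance is given. The final analysis can succeed with 18 events in 145, an observed 12.4%, which is above the rate described as current practice.

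If the wrong figure were used as the goal, the trial would be a different one. If the distance between the two rates were arbitrary, so would be the sample size and the meaning of success.

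**Working it through.** **Inputs, all from Statistical Considerations.** Exact binomial test; overall one-sided alpha 0.025; β = 0.20; expected rate p1 = 0.107; goal p0 = 0.1926; looks at 100 and 145 evaluable subjects with one-sided alphas 0.0068 and 0.0229; loss to follow-up 5%.

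**1. Reproduce the plan's sample size with 10.7% as the expected MAE rate and 19.26% as the goal.**

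Normal approximation: n = [(z_α·√(p0(1−p0)) + z_β·√(p1(1−p1))) / (p0−p1)]² = [(1.960 × 0.3943 + 0.842 × 0.3091) / 0.0856]² = 145.6. The plan has 145.

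Enrolment: 145 / 0.95 = 152.6, rounded up to 153, as stated.

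**2. Reproduce the alphas.** The O'Brien-Fleming-type spending function at information fraction t is 2[1 − Φ(z_0.9875/√t)]. At t = 0.685, the plan's fraction, it spends 0.0068 at the interim and leaves a final nominal level of 0.0229. Both match.

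**3. Exact limits and power.** The limit is the largest count whose lower-tail probability under p0 does not exceed the stage alpha.

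| Look | Count | P(X ≤ count) at 19.26% | Stage alpha | Reject? |
|---|---|---|---|---|
| 100 | 9 | 0.0039 | 0.0068 | yes |
| 100 | 10 | 0.0092 | 0.0068 | no |
| 145 | 18 | 0.0196 | 0.0229 | yes |
| 145 | 19 | 0.0336 | 0.0229 | no |

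Chance of success = P(X₁ ≤ 9) + Σ P(X₁ = x)·P(X₂ ≤ 18 − x) over x = 10 to 18, with X₁ ~ Bin(100, p) and X₂ ~ Bin(45, p).

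- At p = 0.107: 0.7955, against 80% planned.
- At p = 0.1926: 0.0207, within 0.025.

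**4. Try the literal readings.**

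- 10.7% as the share free of MAE: the expected MAE rate is 1 − 0.107 = 0.893, and the chance of 18 or fewer events in 145 is about 3 × 10⁻¹⁰².
- 10.7% as the goal: the limits become 3/100 (P = 0.0044) and 8/145 (P = 0.0226), and the two-stage chance of success at a true 10.7% is 0.0240.

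Neither is compatible with a planned power of 80%. Only the pairing in step 1 returns the plan's figures.

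**5. The distance between the rates.** 0.1926 − 0.107 = 0.0856, and 0.1926 / 0.107 = 1.800. The round ratio suggests a multiplier, but the documents state none, and they state no additive margin either.

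To see how much rests on it, take goals of 1.7 and 1.9 times 10.7% (my assumptions, for range only) and keep the plan's two looks:

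| Goal | Limits at 100 and 145 | Two-stage power at 10.7% |
|---|---|---|
| 18.19% (1.7×) | 8, 16 | 62.3% |
| 19.26% (plan) | 9, 18 | 79.6% |
| 20.33% (1.9×) | 10, 19 | 86.1% |

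The design is sensitive to the goal, as any performance-goal design is. That shows the goal matters; it does not show that 19.26% is wrong.

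**The case for a change.** The strongest case for acting is that the only comparator in the trial is introduced by two sentences that are wrong as written. The named evidence sits next to a rate that is not tested, the tested rate has no shown derivation, and a correction would cost a few words. The slips are in intact, legible text, so they cannot be put down to PDF extraction or redaction. One could also ask the report to say that success shows only an MAE rate below 19.26%, and to give an upper confidence bound at the alpha of the stopping stage. With 10/100 at the interim, for example, the test does not reject, yet a plain 95% upper limit is 17.6%.

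What stands is that the wording is wrong and the derivation is not shown here. The rest does not carry.

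- The tested rate does have a stated source. Study Design attributes the performance goal to previous trials and Statistical Considerations names two of them. What is absent is the calculation.
- A four-page synopsis is not where that calculation must appear. A fuller protocol, not available here, may hold it.
- Rewriting the sentence as 10.7% plus an 8.56-point margin, or tying the trials to 10.7% alone, would put into the protocol facts that the documents do not establish.
- The plan already defines success as rejecting a null that names 19.26%. It claims neither equality with nor improvement on 10.7%, and it mentions no confidence interval. The disclaimer and the stage-matched bound would correct no rule in the plan.
- A pass limit between the expected rate and the goal is normal for this design.

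**Conclusion.** No change to the plan follows. The two slips are clerical: 10.7% is the expected 30-day MAE rate (89.3% would meet the endpoint), and the goal tested is an MAE rate of 19.26%. The hypothesis and the sample-size inputs say so, and the plan's figures reproduce on that reading: 145 evaluable, 153 enrolled, alphas of 0.0068 and 0.0229, and 79.6% two-stage power against 80%. Relabelling the figure would move none of these: the effect on the test, limits, type I error, power and success rule is nil.

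The underived 8.56-point distance is missing detail in a synopsis. It merits at most a question to the sponsor about how 19.26% was reached and which of the two rates the earlier trials support.

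This rests on reading PE as the expected MAE rate, which the reproduced figures support, and on the hypothesis statement governing the analysis, which is the ordinary reading. Whether 19.26% is a well-chosen goal cannot be judged from these pages, and nothing in them shows that it is not.
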